The information and guidance that follow are based on pre-clinical and clinical study results for GSK-manufactured AS03-adjuvanted monovalent pandemic vaccines, post-marketing safety surveillance data seen with unadjuvanted, IIV3s and (in the case of the H1N1 vaccines) post-marketing safety surveillance data seen to date for both PandemrixTM and ArepanrixTM H1N1 vaccines.

The reactogenicity profile in humans of GSK-manufactured AS03-adjuvanted vaccines is primarily associated with the adjuvant. The incidence and severity of injection site redness, swelling, and pain at the injection site in recipients of AS03-adjuvanted vaccines are increased relative to monovalent pandemic influenza antigen alone, a licensed IIV3, or placebo. There is no increase in injection site and systemic reactogenicity events in recipients of AS03-adjuvanted vaccines after a second dose of vaccine relative to the first when given 21 days apart. In young

children (6 months to 6 years old), increased frequency of fever has been observed following a heterologous booster dose of adjuvanted vaccine administered 6 months after the primary series.

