11.6.2 Safety Data

Summaries and analysis of safety data will be presented for the Safety Analysis Population. All summaries and analyses will be presented for all subjects.

Solicited AEs will be summarized by severity for each day after each study vaccination (Days 1-8 post each study vaccination) and as the maximum severity over all 8 days. Additionally, solicited AEs will be analyzed by taking the most severe response over the follow-up period, dichotomizing into a binary variable (none versus mild, moderate, or severe) and using standard techniques, such as exact confidence intervals, to summarize the proportion of subjects reporting each symptom, any injection site symptom, and any systemic symptom. Summaries of solicited AEs will be presented separately for each study vaccination as well as overall study vaccinations by treatment arm. The proportion of subjects reporting symptoms may be compared between

treatment arms using Chi-square or Fisher's exact test. The proportion of subjects reporting solicited symptoms between the different study vaccinations (i.e., first vs. second, first vs. third, second vs. third, as applicable within each study group) will be compared using McNemar's test.

Unsolicited AEs will be coded by Medical Dictionary for Regulatory Activities (MedDRA®) for preferred term and system organ class (SOC). The numbers of SAEs and MAAEs, including NOCMCs and PIMMCs, are likely to be small in this trial and will be reported by detailed listings showing the event description, MedDRA® preferred term and SOC, relevant dates (study vaccinations and AEs), severity, relatedness, and outcome for each event. Non-serious unsolicited AEs will be summarized as number and percentage of subjects reporting at least one event in each MedDRA® preferred term and SOC, cross tabulated by severity and relationship to study product. Additionally, the proportion of subjects and exact 95% CIs of AEs in aggregate and by MedDRA® categories will be computed.

Clinical laboratory data will be summarized by severity for each visit and as the maximum over all post-study vaccination visits. Graphical presentations may include box plots.

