9.3.1. Solicited Events and Symptoms

Systemic solicited adverse events were collected pre-vaccination, and systemic and local solicited adverse events were collected at-least 20 minutes post-vaccination and then daily for 7 days after each vaccination and graded on a scale of 0 (absent), 1 (mild), 2 (moderate) and 3 (severe). Systemic events include fever, feverishness, fatigue, malaise, myalgia, arthralgia, headache, and nausea. Local events include pruritus, ecchymosis, erythema, induration/swelling, pain, and tenderness. Ecchymosis, erythema, and induration are measured by both functional and measurement grading scales as defined in [Table 13](#). The grading scale for systemic events, including quantitative grading for fever, is included in [Table 14](#).

When calculating the incidence of solicited events, each subject will be counted once at the highest severity following the applicable vaccination, and any repetitions will be ignored. For summaries presented separately for each vaccination, the denominator for percentages will be the number of subjects who received the respective vaccination with non-missing data for the event summarized. For summaries over all vaccinations the denominator will be the number of subjects who received at least one vaccination with non-missing data for the event summarized.

The number and percentage of subjects reporting at least one solicited adverse event of each severity will be summarized for each solicited symptom, any systemic symptom, any local symptom, and any symptoms. For each event the denominator is the number of subjects who received the applicable vaccination with non-missing data for the specific event. The 95% CI calculated using Clopper-Pearson methodology from a binomial distribution (SAS Proc Freq with a binomial option) will be presented ([Table 102](#), [Table 103](#), [Table 104](#), [Table 105](#)). Logistic regression models will be fit to estimate the effect of treatment schedule on the

probability of reporting any local event or reporting any systemic event ([Table 106](#), [Table 107](#)). If statistically significant effects are observed in the model for local events or systemic events, then additional models will be fit for each individual event of that type.

$$\text{logit}[P(\text{Event})] = \beta_0 + \beta_1 \times \text{Treatment} + \varepsilon,$$

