For each systemic and local event, any systemic event, any local event, and any solicited event, the maximum severity over 7 days after each vaccination will be summarized for the Safety population. The number and percentage of subjects reporting each event will be summarized by the maximum severity and treatment group, separately for each dose and over all doses. For each event the denominator is the number of subjects who received the applicable vaccination with non-missing data for the specific event. The 95% CI calculated using Clopper-Pearson methodology from a binomial distribution (SAS Proc Freq with a binomial option) will be presented ([Table 108](#), [Table 109](#), [Table 110](#), [Table 111](#)).

The number of subjects reporting a solicited adverse event will be summarized for each day post vaccination for each vaccination and for all vaccinations combined both in a summary table ([Table 112](#), [Table 113](#), [Table 114](#), [Table 115](#)) and graphically in a bar chart ([Figure 52](#) and [Figure 53](#)). A comparison of the event rate for each treatment group between study vaccinations will be presented for those groups receiving multiple vaccinations, including p-values from McNemar's test performed ([Table 116](#), [Table 117](#)).

Systemic and Local solicited events reported by subject will be presented in [Listing 10](#) and [Listing 11](#), sorted by subject ID, vaccination number, parameter, and study day.

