Table 112: Number and Percentage of Subjects Experiencing Solicited Events by Symptom, Severity, Day Post Study Vaccination, and Treatment Arm (Safety Population) – Post Any Study Dose (continued)

Symptom	Severity	Pre-Dose		Post-Dose		Day 1		Day 2		Day 3		Day 4		Day 5		Day 6		Day 7		Day 8+		
		n	%	n	%	n	%	n	%	n	%	n	%	n	%	n	%	n	%	n	%	
Erythema (measurement)	None																					
	Mild																					
	Moderate																					
	Severe																					
Induration/Swelling	None																					
	Mild																					
	Moderate																					
	Severe																					
Induration/Swelling (measurement)	None																					
	Mild																					
	Moderate																					
	Severe																					
[repeat for all treatment groups]																						
N = Number of subjects in the Safety Analysis Population who received the specified dose. Severity is the maximum severity reported post dosing for each subject for each day.																						

Tables with similar format:

Table 113: Number and Percentage of Subjects Experiencing Solicited Events by Symptom, Severity, Day Post Dose, and Treatment Group (Safety Population) – Post Study Dose 1

Table 114: Number and Percentage of Subjects Experiencing Solicited Events by Symptom, Severity, Day Post Dose, and Treatment Group (Safety Population) – Post Study Dose 2

Table 115: Number and Percentage of Subjects Experiencing Solicited Events by Symptom, Severity, Day Post Dose, and Treatment Group (Safety Population) – Post Study Dose 3

Table 116: Comparison of the Number and Percentage of Subjects Experiencing Solicited Systemic Events by Dose and Treatment Group – Safety Population

		Subjects with No Symptoms	Subjects with Mild or Greater Symptoms	Total Number of Subjects n (Percent) [p-value*]
Study Dose 1 vs Study Dose 2				
Group 1: Simultaneous Administration (N=X)	Subjects with No Symptoms	x (%)	x (%)	x (%)
	Subjects with Mild or Greater Symptoms	x (%)	x (%)	x (%)
	Total Number of Subjects	x (%)	x (%)	x (100%) [0.xxx]
Group 2: Sequential Administration (N=X)	Subjects with No Symptoms	x (%)	x (%)	x (%)
	Subjects with Mild or Greater Symptoms	x (%)	x (%)	x (%)
	Total Number of Subjects	x (%)	x (%)	x (100%) [0.xxx]
Study Dose 1 vs Study Dose 3				
Group 2: Sequential Administration (N=X)	Subjects with No Symptoms	x (%)	x (%)	x (%)
	Subjects with Mild or Greater Symptoms	x (%)	x (%)	x (%)
	Total Number of Subjects	x (%)	x (%)	x (100%) [0.xxx]

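### Solicited reactions are compared between schedules and doses only as none versus any grade; a moderate-or-severe contrast added beside the planned tests would be a cheap improvement.

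*Protocol*

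**What the plan says.** Solicited injection-site and systemic reactions through 7 days after each vaccination are a primary safety outcome (Protocol 3.2.1; SAP 3.2.1). SAP 9.3.1 grades each one from 0 (absent) to 3 (severe). The named comparisons are as follows.

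- **Coding.** Protocol 11.6.2 takes the most severe response over follow-up and analyses it by "dichotomizing into a binary variable (none versus mild, moderate, or severe").
- **Between arms, protocol.** The proportion reporting symptoms may be compared between "treatment arms using Chi-square or Fisher's exact test". This comparison is optional.
- **Between arms, SAP.** Section 9.3.1 fits logistic models of treatment schedule on the "probability of reporting any local event or reporting any systemic event" (Tables 106-107, after any study dose).
- **Individual symptoms.** These are modelled only after a significant first result: "If statistically significant effects are observed in the model for local events or systemic events, then additional models will be fit for each individual event". The stated model is again for event yes/no.
- **Between doses.** Protocol 11.6.2 says the proportions after different vaccinations "will be compared using McNemar's test". The shell for Table 116, which Table 117 shares, sets subjects with no symptoms against "Subjects with Mild or Greater Symptoms".

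Severity is reported descriptively. SAP 9.3.1 says each event "will be summarized by the maximum severity and treatment group, separately for each dose and over all doses", with Clopper-Pearson intervals (Tables 108-111). Tables 112-115 and Figures 52-53 give severity by day.

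**The concern.** Protocol 2.3.1 describes the adjuvant's known effect on local reactions as a matter of grade as well as frequency: "The incidence and severity of injection site redness, swelling, and pain at the injection site in recipients of AS03-adjuvanted vaccines are increased" relative to antigen alone, a licensed trivalent vaccine or placebo. The response in Tables 106-107 is any of six local symptoms, or any of eight systemic symptoms, at any grade after any dose. A composite that broad may be common in both adjuvanted groups. If it is, a difference between simultaneous and sequential dosing would show mainly as a move from mild to moderate or severe, and none of the planned tests measures that. The condition on the individual-event models adds to this, because a null any-grade model also ends symptom-level modelling.

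The primary safety objective names sequential or simultaneous administration, and Protocol 2.2 says the trial should inform vaccination programmes about those two options. A reader who takes the schedule comparison from Tables 106-107 would find no estimate of how the schedules differ in moderate or severe reactions.

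**Working it through.** **1. Inputs.** From the documents: 60, 60 and 30 subjects in Groups 1, 2 and 3 (Protocol 11.4.2), and alpha 0.05 without multiplicity adjustment (Protocol 11.4.3). Two-sided testing is stated only for the immunogenicity power tables and is assumed here. No document gives expected reaction rates, so every rate below is an assumption.

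**2. The plan's own safety figure.** Protocol Table 3 (SAP Table 8) gives the chance of seeing at least one event, 1 - (1 - p)^n. For n = 30, 60 and 120:
- p = 10%: 95.8, 99.8, 100.0 (stated 96, >99, >99)
- p = 1%: 26.0, 45.3, 70.1 (stated 26, 45, 70)
- p = 0.1%: 3.0, 5.8, 11.3 (stated 3, 6, 11)
- p = 0.01%: 0.3, 0.6, 1.2 (stated <1, <1, 1)

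The table reproduces. It concerns detecting an event at all. The documents give no power figure for comparing solicited reactions between groups.

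**3. The planned test when only severity differs.** Let any-grade incidence be equal in Groups 1 and 2. All pairs of counts (a, b) from two binomials with n = 60 were enumerated, and the probabilities of pairs with a test statistic above 3.84 were summed. With c = 60 - a and d = 60 - b:
- chi-square: 120(ad - bc)^2 / [60 x 60 x (a + b)(c + d)]
- likelihood-ratio: 2 x sum of O ln(O/E)

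At 95% v 95% the rejection rates are 4.6% (chi-square), 8.1% (likelihood-ratio), 1.1% (Fisher) and 0.4% (Wald test from the logistic model). Because the two rates are equal, these are type I error rates, not power, and they do not change with the moderate/severe split. Across equal any-grade rates from 50% to 95%, chi-square rejects 4.6% to 5.5% of the time.

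**4. A Grade 2-or-higher test on the same subjects.** The same enumeration, using chi-square:

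| Grade 2 or higher | Power |
|---|---|
| 5% v 10% | 17% |
| 10% v 20% | 33% |
| 15% v 30% | 51% |
| 20% v 40% | 68% |
| 25% v 50% | 82% |

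**5. What the report would show at 20% v 40%.** The expected counts are 12/60 and 24/60. Tables 108-111 would display exact intervals of 11-32% and 28-53%. The contrast itself is not planned, but it is simple to compute:
- Risk difference 0.20, SE = sqrt(0.2 x 0.8/60 + 0.4 x 0.6/60) = 0.082, 95% CI 0.04 to 0.36.
- Odds ratio (24 x 48)/(36 x 12) = 2.67, SE of log = sqrt(1/24 + 1/36 + 1/12 + 1/48) = 0.417, 95% CI 1.18 to 6.03.
- Chi-square 120 x (12 x 36 - 24 x 48)^2 / (60 x 60 x 36 x 84) = 5.71.

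The two per-arm intervals overlap although the contrast excludes no difference, so the per-arm intervals do not stand in for it.

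**6. Would an ordinal analysis do better?** Using a rank test as a stand-in for proportional odds (simulated, 60 per arm):
- Any-grade 90% in both arms, Grade 2 or higher 20% v 40%: rank test 49%, Grade 2-or-higher test 68%.
- Grade 2 or higher held fixed, shift from none to mild: at any-grade 50% v 75%, the any-grade test has about 82% and the rank test about 53%. At 70% v 90% the figures are about 80% and 42%.

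No single outcome is best for every kind of shift.

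**The case against.** The strongest reply is that severity is not lost. Protocol 11.6.2 requires summaries by severity for each day and as the maximum, and introduces the dichotomised analysis as an addition. Tables 108-111 give maximum grade by arm with exact intervals, so a reader would see 12/60 against 24/60. The trial also disclaims formal hypothesis testing (Protocol 11.2 and 11.4.3; SAP 6.8), and Grade 3 reactions feed the halting rules in Protocol 9.5. All of this stands, and it limits the weight of the point. It does not supply the missing contrast. The SAP already plans odds ratios and p-values for schedule, but only at the any-grade cut, and the percentage-based halting criteria pool Groups 1 and 2.

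A reader might infer three stronger things that the documents do not support:

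- **That the reactogenicity conclusion rests on an outcome near its ceiling.** No reaction rates are given, and no such conclusion is defined. The ceiling is an assumption.
- **That the protocol predicts more severe reactions under one schedule.** The statement in 2.3.1 compares adjuvanted vaccine with non-adjuvanted controls. Groups 1 and 2 receive the same two adjuvanted doses, so it bears most directly on Group 3, where incidence may differ too. The same section also reports no increase in reactogenicity events after a second adjuvanted dose, which weakens any prediction for the between-dose tests.
- **That an ordinal model should replace the any-grade model.** Step 6 shows that it loses power when the shift is from none to mild.

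**Conclusion.** The gap is real and narrow. Every named comparison of solicited reactions is none versus any grade, the individual-event models depend on that result, and no between-schedule or between-dose estimate exists at moderate or severe. If any-grade incidence is equal and high in Groups 1 and 2, the planned tests cannot register a doubling of Grade 2-or-higher reactions from 20% to 40%, which a direct test would detect about 68% of the time. That figure assumes 60 evaluable subjects per arm, two-sided 5% testing and the stated rates. If Grade 2-or-higher reactions are uncommon, the gain is modest: 17% power at 5% v 10% and 33% at 10% v 20%. Because severity is displayed by arm in a trial that does not claim formal testing, this is a cheap improvement rather than a defect that undermines the safety analysis.

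**What to change.** Keep the any-grade logistic models and McNemar tests, and make two additions in SAP 9.3.1.

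1. **Tables 106-107.** Add the schedule contrast for each subject's maximum functional grade, Grade 2 or higher versus lower, separately for any local and any systemic event. Report an odds ratio or risk difference with its 95% CI. State that it is produced whatever the any-grade model shows, and that the millimetre measurement grades do not count towards it.
2. **Tables 116-117.** Add McNemar's test at Grade 2 or higher beside the mild-or-greater version.

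A proportional-odds model of maximum grade may be reported as well, with its assumption checked, but it should not replace the any-grade model.

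The additions use grades already derived for Tables 108-111, so no new data, visits or subjects are needed, and no clinical rule changes. The costs are SAP wording, a few more p-values in a plan that does not adjust for multiplicity, and wide intervals if such reactions are rare. For example, at 3/60 v 6/60 the difference is 0.05 with SE sqrt(0.05 x 0.95/60 + 0.10 x 0.90/60) = 0.048, giving a 95% CI of -0.04 to 0.14.

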11.6.3 Immunogenicity Data

Summaries and analysis of immunogenicity data will be presented for the mITT and PP populations.

Immune responses in terms of 2017 H7N9 or IIV4 strain-specific HAI and Neut antibody titers will be summarized by treatment arm at each time point. Analyses will include number and percentage of subjects with a titer $\geq 1:40$, number and percentage of subjects achieving seroconversion (defined as either a pre-vaccination titer < 10 and a post-vaccination titer $\geq 1:40$ or a pre-vaccination titer $\geq 1:10$ and a minimum four-fold rise in post-vaccination antibody titer), and GMTs along with corresponding 95% CIs. Descriptive summary statistics will be provided for all assays and time points. The correlation between HAI and Neut antibody titers will be evaluated. Plots such as reverse cumulative distributions or longitudinal presentations of GMTs will be presented.

Additionally, the immune response, as described above, will be summarized by available covariates, such as age, sex, BMI, and prior receipt of seasonal influenza vaccine(s), and these covariates may be considered statistical modeling. As an exploratory analysis, models may be developed to evaluate the relationship between study vaccination schedule and immune response.

Additionally, N1, N2 and N9 NA-specific antibody assays are in development. If successful, N1, N2 and N9 NA-specific responses may be assessed at baseline, 21, 42, 63, and 180 days after receipt of the first study vaccination. For each time point, summaries may include number

and percentage of subjects with detectable N1, N2 and N9 NA response (to be defined in SAP based following assay development and selection) and GMTs along with corresponding 95% CIs. Descriptive summary statistics will be provided for all assays and time points. The correlation of N1, N2 and N9 NA response with HAI and Neut antibody titers will be evaluated, and plots such as reverse cumulative distributions or longitudinal presentations of GMTs will be presented.

Further, a determination of the N9 NA content of the 2017 H7N9 IIV and the N1 and N2 content of seasonal licensed QIV is planned, and if successful, may be used to correlate the N1, N2 and N9 NA elicited antibody responses to the NA content of the 2017 H7N9 IIV and seasonal IIV4, respectively. Detectable NA antibody responses and GMTs will be summarized stratified by NA content, and statistical modeling may be used to examine the relationship of NA response with NA vaccine content, and study vaccination schedule.

At least a subset of samples will also be tested for cross-reactive serum HAI and Neut antibody responses to antigenically drifted variants of influenza A/H7 viruses. Strain-specific results will be summarized using descriptive statistics as described above, correlations with 2017 H7N9 responses, and association with study vaccine dose and adjuvant.

Further immunogenicity testing and/or analyses may be carried out in the future based upon subjects' prior receipt of non-seasonal influenza vaccines, including type (inactivated or live attenuated), what subtype (e.g. A/H3, A/H5, A/H9) and approximate date of vaccination.

11.6.4 Missing Values and Outliers

All attempts will be made to collect all data per protocol. As missing data are expected to be minimal, no imputation will be performed for missing values. Any data point that appears to be erroneous or inexplicable based on clinical judgment will be investigated as a possible outlier. If data points are identified as outliers, sensitivity analyses will be performed to examine the impact of including or excluding the outliers. Any substantive differences in these analyses will be reported.

12 DATA COLLECTION FORMS AND ACCESS TO SOURCE DATA/DOCUMENTS

Each participating VTEU site will maintain appropriate medical and research records for this trial, in compliance with ICH E6, Section 4.9, and regulatory and institutional requirements for the protection of confidentiality of subjects. Each participating VTEU site will permit authorized representatives of the DMID, its designees, and appropriate regulatory agencies to examine (and when required by applicable law, to copy) clinical trial records for the purposes of quality assurance reviews, audits, monitoring and evaluation of the study safety and progress. These representatives will be permitted access to all source data, which include, but are not limited to, hospital records, clinical and office charts, laboratory notes, memoranda, evaluation checklists, pharmacy dispensing records, recorded data from automated instruments, copies or transcriptions certified after verification as being accurate and complete, microfiches, photographic negatives, microfilm or magnetic media, X-rays, and subject files and records kept at the pharmacy, at the laboratories, and medico-technical departments involved in the trial. Source data are all information, original records of clinical findings, observations, or other activities in a clinical trial necessary for the reconstruction and evaluation of the trial.

Interview of subjects is sufficient for obtaining medical history. Solicitation of medical records from the subject's primary care provider is not required.

